Targeting Worry to Improve Sleep

NCT03684057

June 5, 2019

Procedures:

Individuals will be recruited primarily via online advertising (e.g. Facebook and Google AdWords). Those who learn about the study via social media will be prompted to complete an online screening questionnaire. Those who learn about the study via other means (e.g. flyers, word of mouth) will review the questions from the online screener during the initial screening phone call. After the screening call, eligible participants will be scheduled for their baseline visit at the Brown Mindfulness Center ([name]). Study staff will send potential participants a copy of the consent form to review prior to the baseline visit. Participants will be asked to complete four study visits in total: three visits will be in-person and one will be completed online.

At the baseline visit, potential participants will be asked to review the consent form, ask any questions they may have about the study and if they decide to participate in the study, they will be asked to sign the consent form. Study participants will be given a copy of the signed consent form for their records.

Randomization Plan: A research team member who is not involved with the study will prepare sealed envelopes with an individual's group assignment using a block randomization scheme designed by an independent statistician. After the consent process and prior to administration of assessments, study participants will be randomized into one of two groups: 1) Group A – the treatment as usual group; 2) Group B - the UA intervention group. The participant will be given a sealed envelope and asked to open it to determine their group assignment.

Based on the participant's group assignment, the research team member will pull up the appropriate survey in Qualtrics and ask the participant to complete the first portion of the baseline assessment. After they have concluded, they will be instructed on how to complete the shape-matching task and then left alone to complete it on the study laptop while the researcher keeps track of the time from outside.

Upon completion of the assessments, the participant will be instructed to download either the Fitbit app (Group A) or Unwinding Anxiety and the Fitbit app (Group B). Please see below for onboarding specific to group assignment.

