 9. Shape Matching Task. The shape matching task assesses cognitive control, or resistance to distraction. Individuals are presented with probe and target shapes and must decide whether they are the same shape. On some trials a distractor shape will be present, which the individual is instructed to ignore. (approximately 25 minutes)

Module 14 (Group B) or 1 Month (Group A) – Online

- Both groups will receive a personalized survey link via Qualtrics.

1. FFMQ non-reactivity (approximately 1 minute)
2. PSWQ (approximately 3 minutes)
3. MAIA (approximately 5 minutes)
4. PROMIS Sleep & Anxiety (approximately 1 minute)
5. WIS (approximately 1 minute)
6. GAD-7 (approximately 2 minutes)

Module 30 (Group B) or 2 Months (Group A)

- Group A will complete the first five items using a personalized survey link via Qualtrics and the sixth, the GAD-7, will be completed as part of the Unwinding Anxiety assessment.
- Group B will complete the first seven items using a personalized survey link via Qualtrics
- Both groups will complete the shape matching task on a study laptop.
 1. FFMQ non-reactivity (approximately 1 minute)
 2. PSWQ (approximately 3 minutes)
 3. MAIA (approximately 5 minutes)
 4. PROMIS Sleep & Anxiety (approximately 1 minute)
 5. WIS (approximately 1 minute)
 6. GAD-7 (approximately 2 minutes)
 7. Net promoter score (approximately 1 minute)
 8. Shape matching task (approximately 25 minutes)

2 Months post-intervention (Group B) or 4 Months (Group A)

- Both groups will complete the first six items using a personalized survey link via Qualtrics and the shape matching task will be completed on a study laptop.
 1. FFMQ non-reactivity (approximately 1 minute)
 2. PSWQ (approximately 3 minutes)
 3. MAIA (approximately 5 minutes)
 4. PROMIS Sleep & Anxiety (approximately 1 minute)

5. WIS (approximately 1 minute)
6. GAD-7 (approximately 2 minutes)
7. Shape matching task (approximately 25 minutes)

4. Participant Population.

Description of participant population:

We will recruit people who experience sleep disturbances related to anxiety in order to address Aims 1 & 2 of this study. We will recruit people who live within a 30-minute drive of Providence, RI because people who live within close proximity to Providence are more likely to return for follow-up visits and complete the study.

Participants will meet the following criteria:

Inclusion:

1. 18 years or older
2. PSWQ > 40 based on established cut-off suggesting GAD

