The Project Coordinator will check in with participants regarding their experience with the app at 7, 14, and 45 days after they receive access. The purpose of these calls is to encourage engagement with the app in addition to providing a time for the participant to address any questions, comments, likes/dislikes with the Project Coordinator. These will be done via the participants preferred contact method (phone call or text message) and the Project Coordinator will establish preferred times at the baseline assessment. In the event that the Project Coordinator cannot reach the participant, an additional outreach attempt will be made within 24 hours. If this is unsuccessful, no additional contact will be made until the next check-in point. If two consecutive check-ins are missed, an additional email will be sent. Responses may be recorded in Qualtrics and coded solely by participant ID to ensure confidentiality.

5. Recruitment Methods

We will recruit residents who live within a 30-minute drive of Providence, RI primarily using social media advertising (e.g. Facebook, Google AdWords), flyers and info cards, and the Brown Mindfulness Center website.

Social Media

Web page advertisement that briefly describes the study and link to a landing site where potential participants can complete the PSWQ and WIS to determine their eligibility and submit their name, phone number, and email address if interested (see *Landing Page* and *Online Screener* attachments for more details). The contact information will be transferred securely using Stronghold by our Brown-approved consultant, [name] (PSA is already in place). Please see *Social Media Ad* attachment for more details.

Flyers

Physical copies of the flyer will be posted on bulletin boards, in waiting rooms, etc. Digital copies will be provided upon request for use on Facebook, websites, and listservs. Please see *Flyer* attachment for more details.

- Brown University campus and surrounding areas
- RISD campus and surrounding areas
- Cafes, grocery stores (e.g. Whole Foods), community boards

Website

Information about the study will be provided on the Brown Mindfulness Center website along with a link to the landing site where potential participants can determine their eligibility. Please see *MC@B Website Ad* attachment for more details.

Brown Mindfulness Center

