Information about the study will be on display at the Brown Mindfulness Center. This will be a smaller version of the flyer that is easy for individuals to take with them.

Procedure for all recruitment channels

Both the Project Coordinator and Project Director (both CITI/GCP certified) will be responsible for screening potential participants on the phone. This section is denoted in brackets and underlined and does not refer to one individual specifically.

Potential participants enter the screening pipeline either by reaching out to the Project Coordinator directly or by completing the online initial screening questions.

Online screening questions –

Contact information (name, email, and phone number) will only be collected from participants who are deemed eligible by the online screener using survey logic (e.g. PSWQ > 40 and \geq 5/10 on WIS). This will be collected and retained in Qualtrics and only accessed by the Project Coordinator. If an individual is eligible, their contact information will be entered into the key code stored in Stronghold and the study record in Qualtrics will be deleted upon the participant agreeing to participate in the study. If the individual is not eligible after the phone screen, their information will be deleted immediately.

Participants who completed the online screening questions –

Individuals will be screened for eligibility over the phone. The research team member will first describe the study and ask if the individual is interested in moving forward with the screening process. Upon determination of eligibility based on the inclusion/exclusion criteria, the person will be asked again if they wish to participate (see *Phone Screening – Online Screener* attachment for more details). If they are interested in moving forward with the study, the baseline assessment will be scheduled and a copy of the main consent form and directions to the Mindfulness Center at Brown University will be emailed to them (see *MC@B Directions* and *Baseline Scheduling Confirmation Email* attachments).] The online screener should take no more than 5 minutes and the screening call should take no more than 10 minutes.

Participants who did not complete the online screening questions –

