Individuals will be screened for eligibility over the phone. The research team member will first describe the study and if the individual is interested in moving forward with the screening process, verbal consent will be obtained using the bulleted consent form (covered in detail in Part V). Upon determination of eligibility based on the inclusion/exclusion criteria, the person will be asked again if they wish to participate (see *Phone Screening – No Online Screener* attachment for more details). If they are interested in moving forward with the study the same process will be followed as detailed with the group above. In total this process should take approximately 15 minutes.

Screening forms will be kept for eligible participants who will be assigned a participant ID number. This will allow for their medication information to be entered into Qualtrics without identifiers.

Unwinding Anxiety v. Standard of Care Treatment

Unwinding Anxiety is an app-based treatment modality and therefore is unlikely to be identified as regular treatment. However, language has been added to the consent form stating that standard therapy for anxiety symptoms includes medication (such as selective serotonin reuptake inhibitors) and behavioral treatments (such as cognitive behavioral therapy).

While the Principal Investigator (PI) is a clinical psychiatrist, he will not be providing treatment or clinical care, except in the event of an emergency where he is the designed study clinician. In order to diminish any potential of undue influence, the PI will not be in direct contact with the participants on a day-to-day basis.

6. Compensation / Reimbursement

Participants will receive a total of \$100 in Amazon gift cards, if they are eligible for and attend all four assessment visits. They will be given a \$25 Amazon gift card after each assessment (delivered either in-person or electronically depending on assessment type) visit to compensate them for the time involved with each visit. Participants will not be reimbursed for travel. Participants will also have lifetime access to the Unwinding Anxiety app and will be allowed to keep the Fitbit they were given at the baseline visit.

7. Analysis

Participant data will be stored in its deidentified form (coded by unique participant ID). All analyses will be conducted on deidentified data upon completion of data collection. Quantitative data will be analyzed in R, Matlab, and SPSS.

8. Description of the informed consent process:

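### The protocol states no step to keep online screening PSWQ and WIS scores before the Qualtrics record is deleted, and these are the only values of the two outcomes taken before allocation

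*Combined protocol and SAP*

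**What the plan says.** Section 5 (Social Media) says of the study's web page that "potential participants can complete the PSWQ and WIS to determine their eligibility and submit their name, phone number, and email address if interested". Section 4 sets the two score-based entry criteria: "PSWQ > 40 based on established cut-off suggesting GAD", and a WIS of at least 5 out of 10. Both scales are measured again at every visit.

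For a person who passes, section 5 (Online screening questions) says that "their contact information will be entered into the key code stored in Stronghold" and, in the same sentence, that "the study record in Qualtrics will be deleted upon the participant agreeing to participate in the study". Online-screened people then have a phone screen with its own form: "Upon determination of eligibility based on the inclusion/exclusion criteria, the person will be asked again if they wish to participate". After the description of the phone-only route, the protocol adds: "Screening forms will be kept for eligible participants who will be assigned a participant ID number". The reason given is that medication information can then be entered without identifiers.

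The Randomization Plan under Procedures states: "After the consent process and prior to administration of assessments, study participants will be randomized into one of two groups". It then says: "The participant will be given a sealed envelope and asked to open it to determine their group assignment". The Statistical Analysis Plan models change in outcomes by GEE and uses baseline outcome values in the missing-data weights. It does not mention the screening scores.

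**The concern.** PSWQ and WIS are self-reported, and the participant already knows the arm when answering them at the baseline visit. The online screener is answered before that. If it is deleted with only contact details carried over, the trial loses its one measurement of these outcomes that knowledge of the arm cannot have influenced. It also loses the source values for two entry criteria, and no rule re-applies those thresholds at the visit.

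Three things would then be out of reach for online-screened participants: auditing the two scores themselves, seeing whether scores moved differently by arm between screening and baseline, and adjusting for a pre-allocation value. Deletion cannot be undone later.

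**Working it through.** **1. What is carried over.** The screener holds PSWQ answers, WIS answers and contact details. The only transfer described is of contact details. No section of the protocol or the Statistical Analysis Plan describes an export of the scores.

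**2. Does the phone screen replace them?** The opening of Procedures has the screener questions asked by phone only of people who arrive by other means. The stated times fit this:

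- Online route: up to 5 + 10 = 15 minutes (screener plus call).
- Phone-only route: about 15 minutes.
- PSWQ and WIS by the protocol's own estimates: 3 + 1 = 4 minutes, which fits the 5-minute screener.

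Equal totals suggest that the questions are asked once. This is an inference; the phone forms are attachments that are not shown.

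**3. Order of events.** Screener, phone screen, consent, randomisation and envelope, baseline assessments. Every visit value of PSWQ and WIS, baseline included, comes after allocation is known.

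**4. Effect of a shifted baseline.** Let Y be the follow-up score, τ the true arm difference in Y, and let knowledge of the arm add d SD to the reported baseline in one arm (A = 1). The estimated arm difference is then:

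- raw follow-up score: τ, no bias;
- change from the visit baseline, not adjusted for baseline: τ − d;
- change or follow-up adjusted for the visit baseline, with slope β: τ − βd;
- follow-up adjusted for the screening score: τ, because that score precedes allocation.

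The GEE takes change as its outcome. Whether baseline is among its covariates is not stated, so its bias is d or βd.

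**5. Scale, by assumption only.** The documents give no value for d, no SD and no allocation ratio. Assume that the 64 complete data sets split 32 and 32, that d = 0.2, and that the baseline-to-follow-up correlation r is 0.4 to 0.6. The SE of a difference in mean change is √(2/32) × √(2(1 − r)) = 0.25 × √(2(1 − r)):

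| r | SE (SD units) | 0.2 / SE |
|---|---|---|
| 0.4 | 0.25 × 1.095 = 0.274 | 0.73 |
| 0.5 | 0.25 × 1.000 = 0.250 | 0.80 |
| 0.6 | 0.25 × 0.894 = 0.224 | 0.89 |

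With d = 0 the bias is nil.

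**6. What the retained scores could show.** With all 80 enrolled and 40 per arm (assumed), and a screening-to-baseline correlation in the same 0.4 to 0.6 range, the SE of the arm difference in screening-to-baseline change is √(2/40) × √(2(1 − r)). That is 0.224 × 1.095 = 0.245 SD down to 0.224 × 0.894 = 0.200 SD. A table by arm is therefore descriptive and cannot exclude a shift of 0.2 SD. A fall in both arms is expected, because entry selects high scorers; only the difference between arms is informative.

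**The case against.** The strongest reply is that the text may not mean what it literally says. The sentences before the deletion rule concern contact information, so the record in question could be just the identifiable entry. It cannot mean all Qualtrics data, since the visit surveys are held there too. The kept screening forms might also contain the scores, and their stated purpose does not limit their content. This stands as doubt about whether the scores are lost. It does not show that they are kept, and either reading needs the same clarifying sentence.

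A reader might infer that deletion removes the only proof of eligibility. The documents do not support that. Survey logic collects contact details only from people who pass the score thresholds, the phone screen covers the inclusion and exclusion criteria, and screening forms are kept. At most the source scores for two criteria go.

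A reader might also infer that only enrolled people's data are removed. The same paragraph has the information of people found ineligible by phone deleted at once.

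It is also fair to say that any baseline bias comes from randomising before assessment. Deletion does not cause it. It only removes the means of checking for it.

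Precision is a weak argument for the change. An assumed r of 0.4 to 0.6 gives 0.4² = 0.16 to 0.6² = 0.36 of outcome variance, but the visit baseline would explain much of the same variance.

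**Conclusion.** The point holds in a limited form. As written, the protocol deletes the Qualtrics record of online-screened participants and states no step to keep their screening PSWQ and WIS. Given the order of randomisation and assessment, these are the only pre-allocation values of the two outcomes.

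It could affect every participant recruited online, the main channel, and so possibly most of the 80; the number is not stated. The size of any bias is unknown. The 0.2 SD above is an illustration, and the documents do not support a claim that such a shift will occur. The planned 2-month between-group test is untouched if it compares raw scores, which the plan does not specify. No planned analysis depends on the screening scores. What is lost is a check on the change-score GEE and an audit trail for two criteria. Keeping data already collected is a cheap improvement and worth making before records are deleted.

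**What to change.** - **Section 5, Online screening questions.** State that the PSWQ and WIS answers and their date are copied to the coded study database under the participant ID before the record is deleted, and that only name, email and phone are removed.
- **Kept screening forms.** Reconcile this with the sentence on retained forms: say which routes it covers and whether the forms hold the scores. For phone-screened participants, enter the scores from those forms.
- **Statistical Analysis Plan.** Add a sensitivity analysis of follow-up PSWQ and WIS adjusted for the screening score, and a descriptive table of screening-to-baseline change by arm.
- **WIS format.** Entry is scored out of 10, while the visit item asks for a percentage of time. Reconcile the two before using the screening WIS in either analysis.

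The cost is one export per participant, a few sentences of text and possibly one line in the consent form. No visits are added, and the privacy aim is still met because identifiers are removed.

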If the participant is randomized to Group A - They will be given a Fitbit Inspire to track the quality of their sleep and asked to download the Fitbit app to their smartphone. They will be provided with the information necessary to set up their account and instructed how to use the app to track their sleep. Please refer to the included script, *Fitbit Setup Guide* attachment, for more details. They will be asked to wear the Fitbit and record what time they went to bed & woke up in a sleep diary (which will be provided) for one week after the baseline visit, one week before the 3rd visit (in-person), and one week before the 4th visit (in-person). The total number of hours slept per night will be collected for the post-baseline period in Qualtrics via a personalized survey link while data will be collected in person for the other two use periods and recorded in Qualtrics. Upon completion of the third assessment, the UA app will be downloaded to his/her smartphone at no cost and with lifetime access. The participant will be instructed to watch the first module of the app and will review its features with the research team member to ensure they do not have any questions (see *UA Setup Guide* attachment for more details).

If the participant is randomized to Group B - They will be given a Fitbit and the process outlined above will be followed. In addition, the UA app will be downloaded to his/her smartphone and the same process will be followed as outlined above.

Both groups are expected to complete the following tasks / assessments at each research visit:

Baseline – In-person

- Group A will complete the first eight items using a personalized survey link (based on participant ID) via Qualtrics

- Group B will complete the first seven items using a personalized survey link via Qualtrics and the seventh, the GAD-7, will be completed as part of the Unwinding Anxiety assessment.
- Both groups will complete the shape matching task on a study laptop.
 1. Demographics. This form will be filled out in Qualtrics (age, gender, socioeconomic status, employment, education, race/ethnicity, relationship status) (approximately 3 minutes)

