Analyses will be conducted in R using an intent-to-treat approach (ITT). Fischer's exact tests for categorical and Kruskal Wallis tests for continuous variables will be used to determine any between-group differences in baseline demographics. To examine between-group differences in behavioral outcome measures at the primary endpoint (2 months), Welch's t-tests will be used along with Mann Whitney U tests for data that violates the assumption of normality. A series of Generalized Estimating Equations (GEE) will be used to estimate the adjusted intervention effect by regressing change in outcomes at each follow-up on time, group, time*group and confounders identified a priori (using correlation analysis. GEE's are used for longitudinal data in order to account for within-subject covariance over time. False Discovery Rate will be used to correct for multiple comparisons.

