Sleep period time (SPT) will be calculated from the paper sleep diaries (PSDs) by subtracting self-reported bedtime from wake time. Fitbit recorded bedtime, wake time, number of sleep minutes, and number of awake minutes will be used to calculate estimated TST and sleep efficiency (SE). To improve reliability, average estimated TST will only be calculated for participants with ≥ 3 days recorded during each wear period. Analysis will utilize the same approach as described for the behavioral measures with the addition of a complete case (CC) approach; participants who did not complete the baseline wear period will be excluded from analysis. For the ITT analysis, we will compare the robustness of our findings using two statistical approaches for handling missing data. First, we will use inverse probability weighting with propensity scores. This is a two-step method: 1) using logistic regression, the probability of missingness is modeled as a function of baseline covariates and baseline values of the outcome and 2) the inverse of the propensity scores (predicted probabilities of dropout from the first step) serve as weights in our regression model of the outcomes. Provided the data is missing at random (MAR) or that the probability of missingness can be fully explained by observable data, this approach produces asymptotically unbiased estimates. To allow for the possibility that the MAR assumption may not hold, we will also use a second approach, pattern mixture models, in which the distribution of the outcome is assumed to follow a mixture of two distributions: one for those who complete follow up and another for those who do not. We will subsequently examine effects under a per-protocol analysis.

Mediation analyses will be conducted using both the Baron and Kenny four-step approach in addition to causal mediation models. In the causal mediation analysis, we will focus on the natural direct and indirect effects and use the bootstrap method with 1,000 bootstrapped resamples to compute the standard errors and 95% confidence interval.

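### Baseline outcome values are collected but not required as a covariate in the 2-month test or the change-score GEE, which costs precision; the baseline is also recorded after allocation is known

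*Combined protocol and SAP*

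**What the plan says.** The Procedures section lists FFMQ non-reactivity, PSWQ, MAIA, the PROMIS items, WIS, GAD-7 and the shape-matching task at baseline and again at the 2-month assessment.

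The Statistical Analysis Plan then gives two between-group analyses. The first is unadjusted: "To examine between-group differences in behavioral outcome measures at the primary endpoint (2 months), Welch's t-tests will be used", or Mann-Whitney where normality fails. The second is a GEE that estimates the effect by "regressing change in outcomes at each follow-up on time, group, time*group and confounders identified a priori (using correlation analysis". The baseline value of the outcome is not named in either. It could enter the GEE only if the correlation screen picks it. The one place where it is named as a predictor is the inverse-probability weighting step, in which "the probability of missingness is modeled as a function of baseline covariates and baseline values of the outcome".

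The Randomization Plan fixes the order of the baseline visit: "After the consent process and prior to administration of assessments, study participants will be randomized into one of two groups". The participant opens the envelope, so the baseline questionnaires are answered by someone who knows the allocation.

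For the sleep outcomes the SAP says: "Analysis will utilize the same approach as described for the behavioral measures". Their first wear period is the week after the baseline visit, and at that visit participants are "instructed to download either the Fitbit app (Group A) or Unwinding Anxiety and the Fitbit app (Group B".

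**The concern.** In a randomized comparison of a continuous outcome, the baseline value of that outcome is usually the most useful covariate available. Leaving it out of the 2-month test discards information already paid for. Subtracting it, as the change score does, uses it inefficiently unless the correlation is high. The target is only 64 usable data sets and several outcomes share a false-discovery correction, so precision matters here.

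There is a second, linked problem. A baseline recorded after the envelope is opened may itself move with allocation, for example through relief or disappointment. Any analysis that uses such a baseline, by subtraction or by adjustment, can carry that movement into the treatment effect. Adding the covariate without looking at visit order would therefore be incomplete advice.

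**Working it through.** **Inputs from the documents.** 64 usable data sets from 80 enrolled (Participant enrollment target), an implied loss of (80 − 64)/80 = 20%. PSWQ > 40 and WIS ≥ 5/10 for entry, applied at screening (Participant Population; Recruitment Methods). No alpha, power, effect size, SD, correlation or allocation ratio is given, so the plan has no power figure to reproduce.

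**Assumptions.** 32 per arm, two-sided 5% before any false-discovery penalty, true effect 0.60 SD, equal SDs at baseline and follow-up, one follow-up visit, no other covariates. The baseline to 2-month correlation is r.

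**Step 1, variance.** In units of the follow-up variance: raw 1, change 2(1 − r), adjusted 1 − r². The ratios to the adjusted analysis are 1/(1 − r²) for raw and 2(1 − r)/(1 − r²) = 2/(1 + r) for change.

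| r | raw / adjusted | change / adjusted | power raw | power change | power adjusted |
|---|---|---|---|---|---|
| 0.1 | 1/0.99 = 1.01 | 2/1.1 = 1.82 | 66% | 42% | 66% |
| 0.3 | 1/0.91 = 1.10 | 2/1.3 = 1.54 | 66% | 51% | 70% |
| 0.5 | 1/0.75 = 1.33 | 2/1.5 = 1.33 | 66% | 66% | 78% |
| 0.7 | 1/0.51 = 1.96 | 2/1.7 = 1.18 | 66% | 86% | 91% |

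Power is from the noncentral t distribution (62 df, or 61 adjusted). Against the raw test at r = 0.3/0.5/0.7, adjustment makes 64 participants act like 64/0.91 = 70, 64/0.75 = 85 and 64/0.51 = 125.5, about 126. Varying the effect at r = 0.5: with 0.4 SD, raw 35% and adjusted 44%; with 0.8 SD, 88% and 95%.

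**Step 2, entry cut-offs.** PSWQ and WIS are screened and then measured again at the baseline visit, so the selection acts on a separate score. Assume that all three correlations (screening, baseline, 2 months) are 0.6 and the top half is kept. The screening variance falls to 1 − 2/π = 0.363, a reduction of 0.637.
- Baseline and follow-up variance: 1 − 0.36 × 0.637 = 0.771. Covariance: 0.6 − 0.36 × 0.637 = 0.371. Restricted r: 0.371/0.771 = 0.48.
- Adjusted variance: 0.771 − 0.371²/0.771 = 0.592.
- Raw excess: 0.771/0.592 = 1.30, so 30%, down from 1/0.64 = 1.56 (56%).
- Change excess: (0.771 + 0.771 − 2 × 0.371)/0.592 = 0.800/0.592 = 1.35, so 35%, up from 2/1.6 = 1.25 (25%).

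If screening correlates 0.85 with baseline, the change excess is 21%. If the screening score were itself the baseline, it is 9%. The raw loss shrinks in every case (30%, 22%, 20%); the change-score loss can go either way.

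**Step 3, baseline after the envelope.** Assume no true effect and a reporting shift of 0.2 SD in one arm. If it affects baseline only, the bias is 0 for raw, 0.2 for change and 0.2r for adjusted. If it persists to 2 months, the bias is 0.2 for raw, 0 for change and 0.2(1 − r) for adjusted. Type I error at r = 0.3/0.5/0.7:

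| shift | raw | change | adjusted |
|---|---|---|---|
| baseline only | 5% | 10/12/17% | 5.7/7.4/12% |
| persisting | 12% | 5% | 8.9/7.4/6.3% |

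No analysis is immune in both cases.

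**Step 4, null check.** With complete data and a clean baseline, simulated type I error at 32 per arm was 4.7–5.0% for Welch and 4.5–5.2% for the change score.

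**The case against.** The strongest reply is that the GEE may already contain the baseline. If baseline is a candidate and the screen correlates it with change, regression to the mean makes selection very likely: in a simulation with n = 64, p < 0.05 and a 0.6 SD effect, it was selected in 99.9/98/84% of runs at r = 0.3/0.5/0.7. Screened against the follow-up score, the figures were 64/98/100%. This stands as a conditional point, because the SAP states neither the candidates nor the rule. It also supports writing the covariate down, and it does nothing for the unadjusted 2-month test. The reply is also right that 96% is a figure against the raw test only; at that correlation the change score already has 86% power against 91%.

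Three stronger readings are tempting and are not supported.
- A reader might infer that the planned tests are invalid. Omitting a baseline covariate does not bias a randomized comparison. Validity depends on other conditions: a baseline unaffected by allocation for the change score, and loss of up to 16 of 80 that is unrelated to outcome or properly handled. The SAP plans weighting and pattern-mixture models for the latter.
- A reader might infer that the cut-offs make the loss smaller for PSWQ and WIS throughout. Step 2 shows that this is assured only for the raw test.
- A reader might take the percentages as this trial's loss. No correlation or SD is documented for any scale, so they are illustrations.

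**Conclusion.** The point holds as a precision issue with a condition on visit order. Neither planned analysis requires the baseline outcome, although it is collected. Under equal SDs and assumed r = 0.3/0.5/0.7, the raw test carries 10/33/96% excess variance and the change score without the covariate 54/33/18%. At r = 0.1 the gain over the raw test is negligible. The adjusted analysis is at least as precise as either alternative apart from the one degree of freedom.

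The order of the baseline visit decides how clean that gain is. As written, a baseline-only reporting shift passes in full into the change-score GEE and in proportion r into an adjusted model. The documents do not show that such a shift occurs; its size here is assumed. This is worth changing because the remedy is cheap, but it is not a fatal flaw. Confidence is medium, since every size rests on undocumented inputs.

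**What to change.** 1. Complete all baseline behavioral outcome assessments before the envelope is opened, leaving only the expectancy items until after.
2. Make the primary 2-month comparison a model of the 2-month score on that outcome's baseline and group. Require the same baseline covariate in the GEE instead of leaving it to correlation screening. Keep the raw Welch and Mann-Whitney tests as sensitivity analyses.
3. If the visit cannot be reordered, keep the raw 2-month test as lead and report the adjusted model as supportive. For PSWQ and WIS the screening score, taken before randomization, may serve as the covariate if it is kept under the participant ID. Recruitment Methods must first be reconciled: one paragraph deletes the online study record when the person agrees to take part, another keeps screening forms for eligible participants. People who come by other routes "will review the questions from the online screener during the initial screening phone call", so as written the scores may survive only for them. The cut-off acts directly on this covariate, so expect a smaller gain.
4. Do not extend the baseline adjustment to the Fitbit and diary outcomes, whose first week follows Group B's access to the app. Say so where the SAP carries the behavioral approach over to sleep.

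The cost is one degree of freedom per outcome, SAP wording and a reordered visit. Two neighboring matters should be raised separately: the GAD-7 platform differences (for Group B at baseline, "the seventh, the GAD-7, will be completed as part of the Unwinding Anxiety assessment"), and the 4-month visit, which follows Group A's receipt of the app.
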